8.6.4. Eliciting Adverse Event information

The investigator is required to report all directly observed adverse events and all adverse events spontaneously reported by the trial subject using concise medical terminology. In addition, each trial subject will be questioned about the occurrence of adverse events at each study visit (scheduled and non-scheduled) since the time of the last study visit, as well as follow-up from previously recorded adverse event.

8.6.5. Management of Adverse Events

All adverse events will be managed by the investigators according to local treatment guidelines. The sites are equipped with appropriate resources to treat adequately the adverse events. However, in case the patient cannot be managed on site, he/she will be referred for specialized care in the nearest referral hospital.

8.6.6. Adverse Event reporting period

The adverse events reporting period begins upon subject enrolment in the trial (after signature of informed consent) and ends at the end of the subject participation in the trial (D210 follow-up visit).

In this protocol, the reporting period is different for AEs and for SAEs:

- Non-serious adverse events: All non-serious AEs will be reported upon administration of the first dose of trial medication until the end of subject participation in the trial (including post-treatment follow-up period up to D210). Furthermore, non-serious AEs that occur in the screening period (from signature of the informed consent) AND are judged as study-related (e.g. hematoma due to venipuncture) will be reported in the AE CRF.
- Serious adverse events: All SAEs must be reported upon subject enrolment in the trial (after signature of informed consent during screening period) until the end of the subject participation in the trial (including post-treatment follow-up period up to D210).
- Screening failure: beyond the date of screening failure (to be recorded), only serious study-related events will be followed-up.

All adverse events that occur during the adverse event reporting period specified in the protocol must be reported to DNDi, whether or not the event is considered medication related. In addition, any adverse event that occurs subsequent to the adverse event reporting period that the investigator assesses as possibly related to the investigational medication should also be reported as an adverse event.

8.6.7. Adverse Event reporting requirements

Confidential Page 49 of 68

Information on adverse events must be evaluated by a physician. Each adverse event is to be classified by the investigator as serious or non-serious. This classification will determine the reporting procedure for the event to DNDi and Health Authorities/Ethics Committees (as per local regulatory requirements).

All serious adverse events (SAE) are to be reported immediately (within 24 hours of awareness of SAE by the investigator) to DNDi ([contact]), using the SAE report form. This includes a description of the event, onset date and seriousness criteria, duration, severity, relationship to study drugs, outcome, measures taken and all other relevant clinical and laboratory data. The initial report is to be followed by submission of additional information (follow-up SAE form) as it becomes available. Any follow-up reports should be submitted as soon as possible, and if possible within 5 working days.

In addition to immediately reporting SAEs to DNDi, Investigators are responsible for reporting SAEs occurring at their site to the Ethics Committee (IEC), and any periodic safety reporting if applicable, in compliance with the local regulatory requirements.

Serious adverse events should also be reported on the clinical trial adverse event case report form (CRF). It should be noted that the form for reporting of SAE (SAE form) is not the same as the adverse event section of the CRF. Where the same data are collected, the two forms must be completed in a consistent manner, and the same medical terminology should be used.

Non-serious adverse events are to be reported on the CRF, including description of the event, onset date, duration, severity, seriousness, relationship to all study drugs, actions taken and outcome. In the CRF, a given adverse event will be recorded only one time per patient, and the severity recorded will be the maximum level reached. If several distinct episodes of the same condition occur, their number will be recorded in the CRF.

8.6.8. Grading of Adverse Event severity

Severity is a clinical determination of the intensity of an AE. The severity for an AE should be graded using the National Cancer Institute's Common Terminology Criteria for Adverse Events (CTCAE, version 4.03).

In case of AEs that are not described in the CTCAE v4.03, the investigator will use the terminology MILD, MODERATE, SEVERE, LIFE-THREATENING or DEATH to describe the maximum severity of the adverse event as follows:

MILD (grade 1) The subject is aware of the event or symptom, but the event or symptom is easily tolerated (e.g. no reduction in daily activities is required)

MODERATE (grade 2) The subject experiences sufficient discomfort to interfere with or reduces his or her usual level of activity.

SEVERE (grade 3) Significant impairment of functioning: the subject is unable to carry out usual activities and/or the subject's life is at risk from the event

Confidential Page 50 of 68

LIFE-THREATENING (grade 4) The subject is at risk of death at the time of the adverse event. It does not refer to an AE that hypothetically might have caused death if more severe (Life-threatening consequences, urgent intervention required)

DEATH (grade 5) Death related to AE

This information on AE grading will be entered in the adverse event CRF.

It is to be noted the distinction between severity (intensity) and seriousness (regulatory definition) of adverse events. A severe adverse event is not necessarily a serious adverse event.

8.6.9. Adverse Event causality assessment

For both serious and non-serious adverse events, the investigator is required to assess if there is a causal relationship between the adverse event and all the study drugs, i.e. to determine whether **there is at least a reasonable possibility** that one of both study drugs caused or contributed to the adverse event. This means that there are facts and arguments to suggest a causal relationship.

To help investigators with the decision binary tree in the evaluation of causality, the CIOMS VI group recommends that investigators be asked to consider the following before reaching a decision:

- Medical history
- Lack of efficacy/worsening of existing condition
- Study medications
- Other medications (concomitant or previous)
- Withdrawal of study medication, especially following trial discontinuation / end of study medication
- Erroneous treatment with study medication (or concomitant)
- Protocol related procedure

Using this information the investigator will classify each adverse event as:

Not related: There is no reasonable possibility of causal relationship

between an AE and study drug

Related: There is at least a reasonable possibility of a causal relationship

between an AE and a study drug. This means that there are facts

(evidence) or arguments to suggest a causal relationship.

The decision to suspend, and resume treatment or to permanently interrupt treatment due to an adverse event will be left to the clinician in charge.

8.6.10. Exposure in utero

Confidential Page 51 of 68

All female patients of child bearing age will be excluded unless they agree to undergo a pregnancy test and explicitly consent to take an acceptable method of contraception (i.e. Depo-Provera). Urine pregnancy tests will be performed in woman of child-bearing potential at baseline to exclude any pregnancy, and on D28, D56 and D210 visits to monitor eventual unexpected pregnancy. All pregnant women will be excluded from the study. This criterion was set because of the teratogenic potential of MF (demonstrated in rats). The effective contraception should be used for a minimum period of 5 months after end of treatment with MF. Therefore, Depo-Provera injection will be required before treatment onset and around day 90 to cover for the entire exposure period.

However, in the unlikely event that any trial subject becomes or is found to be pregnant while receiving any of the study treatment drugs or during follow-up period, the investigator must submit the event on a Pregnancy report form. The information submitted should include the anticipated date of delivery.

The investigator will follow the subject until completion of the pregnancy or until pregnancy termination (i.e., induced / spontaneous abortion). The investigator will provide pregnancy outcome information on a Pregnancy outcome form.

A pregnancy is not an SAE.

In the case of a live birth, a medically qualified person should assess the infant at the time of birth and submit a Child report. An SAE should be declared in the case of unfavorable pregnancy outcome (abortion, still birth) or congenital abnormality (in addition to the Child report).

8.6.11. Adverse event follow up

All adverse events should be followed until they are resolved or the investigator assesses them as chronic or stable or the subject participation in the trial ends (i.e., until a final report is completed for that subject).

In addition, all serious adverse events and those non-serious events assessed by the investigator as possibly related to the investigational drug must continue to be followed even after the subject participation in the trial is over. Such events should be followed until they resolve or until the investigator assesses them as "chronic" or "stable." Resolution of such events is to be documented on the CRF and SAE form.

9. Withdrawal criteria

A subject should be withdrawn from the study treatment if, in the opinion of the investigator, it is medically necessary, or if it is the wish of the subject.

If a subject does not return for a scheduled visit, every effort should be made to contact the subject.

In any circumstance, every effort should be made to document subject outcome, if possible.

If the subject withdraws consent, no further evaluations should be performed and no attempts should be made to collect additional data, with the exception of safety data,

Confidential Page 52 of 68

which should be collected if possible and in accordance with patient consent.

If a subject withdraws from the study, the reason must be noted on the CRF.

If a subject is withdrawn from the study because of a treatment limiting adverse event, thorough efforts should be made to clearly document the outcome of AE.

9.1. Rules in case of treatment suspension or interruption

In the event that treatment is interrupted (e.g. due to an adverse event), the decision to resume treatment will be taken by the site Principal Investigator.

If treatment interruption lasts > 72hs due to an AE related to MF, or if treatment needs to be interrupted due to an AE related to PM or SSG, rescue treatment will be considered, at the discretion of the investigator.

Once rescue treatment is given, the patient will be considered a treatment failure, and will be withdrawn from the study.

If rescue treatment is not indicated, the patient may continue to participate in the study, and perform the scheduled visits and procedures.

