2.2.2. Secondary Endpoint(s)

Safety:

Frequency of SAEs and AEs requiring treatment discontinuation.

Frequency and severity of adverse events from the start of treatment through the last visit, at D210.

Efficacy:

Initial cure - cure at the end of treatment (Day 28), defined as recovery of clinical signs and symptoms; absence of parasites (microscopy) and no rescue treatment administered up to and including Day 28.

Probable cure - absence of clinical signs and symptoms of VL at D56 and no prior requirement for rescue treatment.

Pharmacokinetics:

Total and partial blood plasma exposure to PM and MF (bioanalysis performed by a validated LC-MS/MS assay), defined as the area under the concentration-time curve, for MF, during treatment and until the last point of follow-up, and for PM based on full curves both on the first day of treatment (day 1) and the last day of treatment (day 14).

Pharmacodynamics:

Blood parasite clearance over time (qualitative and quantitative), as measured by qPCR from blood samples, from baseline until day 210, and at any suspicion of relapse during the trial.

Tissue parasite loads, as semi-quantified by microscopy and qPCR from tissue samples collected at baseline, at the end of treatment (D28) and at any suspicion of relapse during the trial.

 Compliance to MF treatment in an outpatient setting will be described through patients' hospital records history, drug accountability and PK measurements.

3. Study design and study design rationale

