7.8. Rescue treatment

In case of treatment failure or intolerability (treatment must be permanently interrupted), rescue treatment will be provided to the patient, at the discretion of the study physician and based on the national VL treatment guidelines. For patients in arm 1 and 2, rescue treatment is expected to be SSG/PM (SSG 20 mg/kg/day, PM 15 mg/kg/day) or AmBisome multiple dose (30 mg/kg total dose). In arm 3, rescue treatment is expected to be AmBisome multiple dose (30 mg/kg total dose).

Patients will be given rescue treatment if they have:

- failed to respond to MF/PM treatment or to SSG/PM reference treatment within the treatment period (lack of improvement or worsening of the clinical signs and symptoms of VL).
- failed to respond to MF/PM treatment or to SSG/PM reference treatment at the EOT assessments (D28). This will be reflected by positive parasitological assessment and/or lack of improvement or worsening of the clinical signs and symptoms of VL.
- failed to tolerate trial medication / occurrence of adverse event(s) during receipt of trial drugs that requires permanent treatment interruption, and rescue treatment is indicated by the investigator (see section 9).
- relapsed, i.e. recurrence of symptoms, signs and presence of parasites after EOT

Confidential Page 38 of 68

(D28) during the follow up period

• developed severe post kala azar dermal leishmaniasis (PKDL) that necessitates rescue treatment (see section 8.3.4).

8. Study Assessments

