8.5. Assessment of Safety

Safety of the different treatment regimens will be assessed through routine monitoring of adverse events. At each study visit, the patients will be enquired about current adverse events or any events observed during the period previous to the visit. In addition, evaluation of hematology and blood chemistry parameters, regular measurement of vital signs and physical examinations will be made at scheduled follow-up visit.

Audiometric test will be performed at baseline and on days 14, 28 and 210 for all patients.

ECG will be performed at baseline and on day 14 in all arms, and in addition on days

Confidential Page 45 of 68

7 and 28 in the reference arm SSG/PM. SOPs will be developed to guide investigators on audiometry and ECG assessments.

Urine pregnancy tests will be performed in woman of child-bearing potential at baseline to exclude any pregnancy, and on D28, D56 and D210 visits to monitor eventual unexpected pregnancy.

HIV test will be repeated at the D210 visit only for patients in Gondar and Abdurafi sites, due to high prevalence of HIV/VL co-infected patients (15%) in this specific population.

The frequency and severity of AEs will be described, as well as frequency of SAEs or AEs that lead to treatment discontinuation. See section 8.6 for AE definition and reporting.

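### Section 9.1 withdraws rescued patients from the study, so scheduled safety follow-up to D210 stops for them and reporting of new unrelated events is left unclear

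*Combined protocol and SAP*

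**What the plan says.** Section 9.1 counts a patient given rescue as a treatment failure who "will be withdrawn from the study". The sentence after it gives the contrast: "If rescue treatment is not indicated, the patient may continue to participate in the study, and perform the scheduled visits and procedures".

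Other sections plan safety assessment to the end of the trial without exempting rescued patients. Section 2.2.2 lists as a safety endpoint "Frequency and severity of adverse events from the start of treatment through the last visit, at D210". Section 8.5 states: "Audiometric test will be performed at baseline and on days 14, 28 and 210 for all patients". Section 10.7 puts every enrolled patient with at least one dose into the safety analysis.

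On reporting, section 8.6.6 has SAEs reported "until the end of the subject participation in the trial (including post-treatment follow-up period up to D210"). Its rule for late events, which makes them reportable as AEs too, begins: "any adverse event that occurs subsequent to the adverse event reporting period that the investigator assesses as possibly related to the investigational medication should also". Section 8.6.11 keeps following SAEs, and non-serious events possibly related to the investigational drug, after participation ends. Section 9 asks for every effort to document the patient's outcome, and for the outcome of any treatment-limiting AE that led to withdrawal.

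On rescue drugs, section 7.8 says: "For patients in arm 1 and 2, rescue treatment is expected to be SSG/PM" or multiple-dose AmBisome. In arm 3 only AmBisome is expected.

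**The concern.** Scoring a rescued patient as a failure settles the efficacy outcome. It gives no reason to end safety observation, yet section 9.1 joins the two. The patients who lose follow-up are not a random subset: they are those who did not respond, relapsed or did not tolerate treatment. The drugs they are then expected to receive also differ by arm. In arm 1 the expected options include SSG/PM, which means SSG and a further course of paromomycin. Section 1 lists reversible ototoxicity as a known effect of paromomycin, and D210 is the only scheduled audiometry after D28.

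At stake is whether AE and SAE frequencies through D210 can be reported on the same footing for all dosed patients in both arms. Section 10.7 says these comparisons feed the benefit-risk assessment. It does not say how events after rescue are counted or attributed.

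**Working it through.** No figure in the plan rests on this point, so there is none to reproduce. The check has two parts.

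**1. What happens to each kind of safety information after rescue**

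- SAE already open at rescue: followed under section 8.6.11. Covered.
- Non-serious AE already open and possibly related: followed under section 8.6.11. Covered.
- AE that led to withdrawal: outcome to be documented under section 9. Covered.
- New event judged possibly related to the investigational medication: reportable under section 8.6.6 even after the reporting period. Covered if it comes to the site's attention, but no visit is scheduled at which to ask. The trial is open label (section 7.6), so the relatedness judgement is made knowing the arm and the rescue drug. The text does not say whether the term includes SSG-PM given as the reference treatment in arm 3.
- Subject outcome, including death: best effort under section 9, with no scheduled contact.
- New SAE or death judged unrelated: section 8.6.6 ends reporting with the subject's participation and describes that as including follow-up to D210. It does not say which governs when participation ends early through withdrawal. Unclear.
- New non-serious AE judged unrelated: same ambiguity, and no scheduled questioning.
- Audiometry at D210, and the haematology and pregnancy tests at D56 and D210 (section 5): no visit, so not done.

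The firm loss is the scheduled visits. The uncertain part is new events not judged related.

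**2. How many patients**

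Inputs from section 10.1: 170 patients in each of arms 1 and 3; expected cure 93% in arm 1 and 91% in arm 3. Arm 2 is left out because recruitment to it has stopped and it is only described.

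Upper bound, taking every failure as rescued:

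- Arm 1: 170 × (1 − 0.93) = 11.9
- Arm 3: 170 × (1 − 0.91) = 15.3
- Total: 11.9 + 15.3 = 27.2, and 27.2 / 340 = 8.0%

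Not every failure is rescued. Section 10.6 also counts as failures patients lost to follow-up by D56, deaths during treatment and VL-related deaths in follow-up. The documents do not give the rescued share, so I assume 50% to 100%:

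- Arm 1: 11.9 × 0.5 = 5.95, up to 11.9
- Arm 3: 15.3 × 0.5 = 7.65, up to 15.3
- Total: 13.6 to 27.2, about 14 to 27 patients

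Follow-up lost per patient depends on timing. After D28 the only scheduled visits are D56 and D210.

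- Rescue during the treatment period loses the rest of that period's visits, D28, D56 and D210.
- Failure at D28 loses D56 and D210.
- Relapse after D56 loses D210 only.
- Relapse found at D210 loses nothing.

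A patient who relapses after D28 keeps the D14 and D28 audiometry.

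**The case against.** The strongest reply is that the protocol does not switch safety reporting off. A reader of section 9.1 alone might infer that SAEs and deaths after rescue are not collected. Sections 8.6.6, 8.6.11 and 9 do not support that: open SAEs are followed, later possibly related events are reported, and outcome is to be documented as far as possible. Section 9 even allows safety data to be collected, where the patient agrees, after consent is withdrawn. This part of the reply stands, and it confines the point to scheduled visits and to new events not judged related.

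A second reply concerns scope. Section 9.1 is headed as a rule for treatment suspension or interruption, and section 7.8, which covers non-response, relapse and severe PKDL, does not mention withdrawal. That is a fair ambiguity. But the sentence in 9.1 carries no qualifier, and no other section provides for visits after rescue.

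Third, a reader might apply 7% or 9% to both arms and quote 24 to 31 patients (340 × 7% = 23.8; 340 × 9% = 30.6). The plan's arm-specific rates give 27, and only as an upper bound. One SAE is 1/170 = 0.59 percentage points of an arm, but that scales a single event and does not show that any is missed.

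Fourth, a reader might argue that the loss weakens the justification of the 7% margin. Section 10.6 bases the margin on expert consultation and advantages expected in advance (removal of the antimonial, fewer injections, a shorter stay, suitability in remote areas), not on this trial's safety comparison.

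Finally, events after rescue are confounded by the rescue drug, so D210 audiometry after rescue would not isolate the assigned regimen. That is true. It is a reason to show results both up to rescue and through D210, which requires that the data exist.

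**Conclusion.** The point holds as a conflict to be reconciled and a cheap improvement. Read as written, section 9.1 ends scheduled safety visits at rescue, contrary to the D210 safety endpoint in 2.2.2, audiometry for all patients in 8.5 and the all-dosed safety set in 10.7. New deaths, SAEs and AEs after rescue that are not judged related then have no scheduled collection, and it is unclear whether they are reportable to D210.

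The size is at most about 12 patients in arm 1 and 15 in arm 3 (27 of 340, 8%), or about 14 to 27 if 50% to 100% of failures are rescued. This rests on the planned cure rates, on the unqualified reading of 9.1, and on an assumed rescued share. For late relapses the loss is one visit or none.

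The primary endpoint is not affected. The loss is selective, because it falls on failures and intolerant patients, but the documents do not establish the direction of any bias in the safety comparison.

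**What to change.** Reconcile sections 2.2.2, 8.5, 8.6.6, 8.6.11, 9, 9.1 and 10.7 so that treatment failure is kept apart from withdrawal from the study:

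- In 9.1, state that a rescued patient is scored a treatment failure and leaves study treatment but, subject to consent, stays in the already scheduled follow-up to D210 for vital status, SAEs and audiometry.
- In 8.6.6, state when the reporting period ends for a rescued patient, and whether the late-event rule covers the reference treatment.
- In 10.7, tabulate AEs both up to rescue and through D210, with post-rescue events flagged.

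Rescue care itself is unchanged. The cost is the remaining scheduled visits for at most about 8% of patients in arms 1 and 3: usually one or two, plus D28 and any remaining treatment-period visits if rescue comes earlier. Events after rescue will be confounded by the rescue drug, so the through-D210 table needs that caveat.
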